3. INTRODUCTION

As per ICH E9^[1], the purpose of this document is to provide a more technical and detailed elaboration of the principal features of the analysis described in the protocol, and to include detailed procedures for executing the statistical analysis of the primary and secondary variables and other data.

This TSAP assumes familiarity with the Clinical Trial Protocol (CTP), including Protocol Amendments. In particular, the TSAP is based on the planned analysis specification as written in CTP Section 9 “Statistical Methods and Determination of Sample Size”. Therefore, TSAP readers may consult the CTP for more background information on the study, e.g., on study objectives, study design and population, treatments, definition of measurements and variables, planning of sample size, randomization.

SAS® Version 9.3 or higher will be used for all analyses.

4. CHANGES IN THE PLANNED ANALYSIS OF THE STUDY

- New analyses set, which is not mentioned in the protocol (Details are displayed in TSAP Section 6.3):
 - Full analysis set (FAS)

5. ENDPOINT(S)

5.1 PRIMARY ENDPOINT(S)

The primary endpoint of the presented study is “therapeutic success” at visit 2 i.e. approximately 6 weeks after starting treatment, defined as 10-point increase in the PF-10 score between visit 1 and visit 2.

5.2 SECONDARY ENDPOINT(S)

- Absolute changes in PF-10 score from visit 1 to visit 2
- General condition of the patient, evaluated by the physician (PGE score) at visit 1 and visit 2
- Patient satisfaction with Spiolto® Respimat® at visit 2

5.3 FURTHER ENDPOINT(S)

None.

5.4 OTHER VARIABLE(S)

Other variables will be baseline characteristics and patient's characteristics such as age, gender, height and weight. Additionally information about concomitant medication, diseases, therapy data, further therapies and comorbidities will be collected as well as about smoking status, exacerbation history, mMRC and GOLD group.

6. GENERAL ANALYSIS DEFINITIONS

6.1 TREATMENT(S)

In the presented study, treatment with Spiolto® Respimat® will be according to product information.

6.2 IMPORTANT PROTOCOL VIOLATIONS

Table 6.2: 1 defines the different categories of important protocol violations (PVs). The final column describes which PVs will be used to exclude subjects from the different patient analysis sets^[2].

Table 6.2: 1 Important protocol violations

Category/ Code	Description		Requirements	Excluded from
A		Entrance criteria not met		
	A1.1	Inclusion criterion 2 (Age >=40 years)	Not met as specified in the protocol	None
	A1.2	Inclusion criterion 3 (Patients diagnosed with COPD and requiring long-acting dual bronchodilation (LAMA+LABA) treatment according to approved Spiolto® Respimat® SmPC and COPD GOLD guideline recommendation)	Not met as specified in the protocol	None
	A2.1	Exclusion criterion 1 (Patients with contraindications according to Spiolto® Respimat® SmPC)	Met as specified in the protocol	None
	A2.2	Exclusion criterion 2 (Patients who have been treated with a LABA/LAMA combination (free and fixed dose) in the previous 6 months)	Met as specified in the protocol	None
	A2.3	Exclusion criterion 3 (Patients continuing LABA-ICS treatment should not be additionally treated with Spiolto® Respimat® in order to avoid a double dosing of long-acting beta-agonists)	Met as specified in the protocol	None
	A2.4	Exclusion criterion 4 (Patients for whom further follow-up is not possible at the enrolling site during the planned study period of approx.. 6 weeks)	Met as specified in the protocol	None
	A2.5	Exclusion criterion 5 (Pregnancy and lactation)	Met as specified in the protocol	None
	A2.6	Exclusion criterion 6 (Patients currently listed for lung transplantation)	Met as specified in the protocol	None
	A2.7	Exclusion criterion 7 (Current participation in any clinical trial or any other non-interventional study of a drug or device)	Met as specified in the protocol	None
B		Informed consent		
	B1	Informed consent not available/not done	IC 01 not met as specified in the protocol	All

Category/ Code	Description	Requirements	Excluded from
	(Inclusion criterion 1)	or informed consent date missing	

[figure not shown]
6.3 PATIENT SETS ANALYSED

Full analysis set (FAS): All screened patients with informed consent, date of registration, at least one documented administration of Spiolto® Respimat® and available PF-10 score at visit 1 and visit 2.

Treated set (TS): All screened patients with informed consent, date of registration and at least one documented administration of Spiolto® Respimat®.

Table 6.3: 1 Patient sets analysed

Class of endpoint	Patient set	
	TS	FAS
Primary and secondary endpoints		X
Safety endpoints	X	
Demographic/baseline	X	

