9. RESEARCH METHODS

9.1 STUDY DESIGN

This is a self-controlled study design enrolling consented COPD patients who will be treated with Spiolto® Respimat® according to the approved SmPC.

Patients will be enrolled consecutively and will be followed over an observational period of approx. 6 weeks. Data as listed in table 9.1:1 will be collected.

Table 9.1:1: Visit flow chart and data collection parameters

Parameter	Visit 1; baseline visit	Visit 2; approx. 6 weeks after baseline visit
Informed Consent	X	
Inclusion / Exclusion Criteria	X	
Patient demographics (age, gender, height, and weight)	X	
Start of COPD	X	
Number of exacerbations in the last 12 months	X	
Number of exacerbations leading to hospitalization in the last 12 months	X	
mMRC breathlessness scale, completed by the patient	X	
Past COPD therapies (6 months before visit 1)	X	
Respimat® training (yes/no)	X	
COPD severity based on GOLD assessment ¹	X	
Smoking status/history	X	X
Concomitant diseases / Comorbidities	X	X
COPD related and other relevant concomitant medication	X	X
Physical functioning (PF-10) questionnaire, completed by the patient	X	X
General condition of patient evaluated by Physician's Global Evaluation (PGE)	X	X
Safety: Adverse Drug Reactions (serious and non-serious), fatal AE, pregnancy	X	X
Patient satisfaction with Spiolto® Respimat®, completed by the patient		X
Rational for Spiolto® Respimat® treatment discontinuation (if applicable)		X
Continuation or discontinuation of treatment with Spiolto® Respimat® after the study (yes/no)		X

¹ GOLD patient group (A, B, C or D) will be automatically calculated within the eCRF based on available exacerbation history, mMRC, and GOLD spirometric classification of airflow limitation based on post-bronchodilator FEV₁ if available.

Baseline characteristics of patients being eligible and who gave Informed Consent, but were not treated in the study will also be collected.

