9.5 STUDY SIZE

In a previous study, 205.426 with over 1000 patients treated with Spiriva[®] Respimat[®], therapeutic success (i.e., 10-point increase in the PF-10 score between visit 1 and visit 2) was achieved in 61% of the patients.

In this study, a lower therapeutic success rate is expected as patients may be already on maintenance treatment at baseline. Assuming a 50% therapeutic success rate and 6510 patients, the 95% confidence interval for the therapeutic success rate would be between 48.8% (lower limit) and 51.2% (upper limit).

To account for a 7% drop-out rate, the sample size becomes 7000 patients.

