9.7.3 Planned analyses

All patients who have received at least one dose of Spiolto® Respimat® will be included in the analysis; this is the treated set. All analyses will be performed on the treated set (as-treated analysis). If patients have missing values for an outcome, those patients will be excluded for that outcome's analysis.

The assessment will be carried out using SAS® software. The statistical characteristics presented in the end-of-text tables will be N / mean / SD / min / median / max for continuous variables. Tabulations of relative and absolute frequencies will be presented for categorical variables. Incidence rates and 95% CI will be given when appropriate.

The analyses will relate to the following data as recorded in the eCRF:

- Patient demographics (age, gender, height, and weight)
- Comorbidities
- COPD related and other concomitant medication
- History of smoking
- Reported exacerbations
- Breathlessness based on mMRC score
- Physical Functioning based on PF-10 scores (therapeutic success at visit 2); primary outcome
- Changes from visit 1 to visit 2 in the PF-10 score; secondary outcome
- Patient satisfaction with Spiolto® Respimat® at visit 2 only; secondary outcome
- General condition of the patient: evaluated by the physician (Physician's Global Evaluation (PGE)); secondary outcome
- Adverse Drug Reactions (ADR & SADR), fatal AEs, pregnancies
- GOLD spirometric classification (1,2, 3, 4)
- GOLD patient groups (A, B, C, D)
- Details of treatment with inhaled respiratory agents before the study
- Details of treatment with respiratory agents during the study

- Reasons for ending treatment during the observation period
- Details of treatment continuation / discontinuation

Main analysis

For the primary outcome, the proportion of patients with therapeutic success will be presented together with the 95% confidence interval.

Further analyses

The patient's general condition (PGE) at visit 1 and visit 2, mMRC at visit 1 and patient satisfaction at visit 2 are categorical variables so they will be analyzed as tabulations of frequencies. Change from visit 1 to visit 2 in the PF-10 score is a continuous outcome, so it will be analyzed with N / mean / SD / min / median / max.

The safety data will be reported according to local requirements.

As similar studies will also be performed in other European countries, data pooling might be considered at the end.

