9.7.4 Handling of missing data

If less than half of the PF-10 questions are missing for a patient, the missing values will be replaced with the mean of the other values and the PF-10 score will be calculated. If half or more than half of the PF-10 questions are missing, no score will be calculated and the PF-10 score will be marked as missing. No other missing data will be imputed. Every effort will be made to collect complete data at the specified time points. Any removal from the analysis will be documented, stating the site and patient number as well as the reason for removal.

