6.6 HANDLING OF MISSING DATA AND OUTLIERS

In context of PF-10 questionnaire, missing values will be replaced with the mean of the other values, if less than half of the questions are missing for a patient. If half or more than half of the questions are missing, no score will be calculated and the PF-10 score will be marked as missing. No other missing data will be imputed.

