7.1 DEMOGRAPHIC AND OTHER BASELINE CHARACTERISTICS

Only descriptive statistics are planned for this section of the report. All baseline analyses will be done for the treated set.

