7.3 PRIMARY ENDPOINT

For the primary endpoint, the percentage of patients with therapeutic success will be presented together with the 95% confidence interval. The number and percentage of patients with and without therapeutic success will be calculated for the whole FAS set [REDACTED]

[REDACTED]

[REDACTED]

[figure not shown]
The PF-10, represented by the physical functioning subscale of the Short Form 36 (SF-36), ranges from 0 to 100. A higher score indicates a better physical functioning. The score is calculated as followed:

Answer to questions 01- 10	Score
Yes, limited a lot	1
Yes, limited a little	2
No, not limited at all	3

Transformed scale = [(Sum of final item values – 10) * 100] / 20

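### The primary success rate counts only patients with a PF-10 score at both visits, and no readable text tests how far treated patients without a visit-2 score could move it

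*SAP*

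**What the plan says.** SAP 6.3 defines two sets. The treated set needs consent, a registration date and at least one documented administration. The FAS needs all of that plus an "available PF-10 score at visit 1 and visit 2". Table 6.3:1 assigns the primary and secondary endpoints to the FAS, and safety and baseline data to the treated set. SAP 7.3 follows this: "The number and percentage of patients with and without therapeutic success will be calculated for the whole FAS set".

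On missing data, SAP 6.6 replaces single PF-10 items by the mean of the others when fewer than half are missing. Beyond that, "No other missing data will be imputed". On baseline tables, SAP 7.1 says: "All baseline analyses will be done for the treated set".

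Protocol 9.7.3 names the treated set as the population for all analyses but adds: "If patients have missing values for an outcome, those patients will be excluded" from the analysis of that outcome. For the primary endpoint this gives the same denominator as the FAS. Two protocol provisions bear on the excluded patients. Section 9.7.4 states "Any removal from the analysis will be documented, stating the site and patient number as well as the reason for removal", and section 9.7.3 lists the reasons for ending treatment among the data to be analysed. Section 9.5 expects the loss: "To account for a 7% drop-out rate, the sample size becomes 7000 patients".

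**The concern.** The FAS is defined partly by the outcome it is used to estimate. A treated patient with a baseline PF-10 who dies, or who stops and does not return, leaves both numerator and denominator. A patient who stops treatment but completes the PF-10 at visit 2 stays in. What matters is whether the visit-2 score exists, and that may well be related to how the patient fared.

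With no comparator and no hypothesis test (protocol 9.7.2), the primary result is one percentage with its interval, and the width of that interval is the stated basis for the study size. The interval describes sampling error among patients who returned a score and takes no account of those who did not. If patients who do badly are less likely to return, the reported rate is too high for treated patients as a whole, and nothing in the readable output would show by how much. The reasons for removal and for ending treatment say why patients are absent, not how far the percentage could move. Because baseline tables cover the treated set only, a reader also cannot see whether excluded patients differed at the start.

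**Working it through.** **Inputs** (protocol 9.5): assumed success rate p = 0.50; evaluable n = 6510; stated 95% CI 48.8% to 51.2%; drop-out d = 7%; total N = 7000. The success rate q among patients without a visit-2 score is not in the documents, so it is varied over its whole range.

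**1. The plan's own figures.**
- Half-width = 1.96 × √(0.50 × 0.50 / 6510) = 0.0121, or 1.21 points, giving 48.8% to 51.2% as stated.
- 7000 × 0.93 = 6510, so 7000 − 6510 = 490 patients are expected to be missing.

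**2. Effect of the missing patients.** The rate over all treated patients is (1 − d)p + dq. The FAS rate p exceeds it by d(p − q). With d = 0.07 and p = 0.50 the all-treated rate is 0.465 + 0.07q:

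| Assumed q | All-treated rate | Shift from 50% (points) |
|---|---|---|
| 0% | 46.5% | −3.5 |
| 20% | 47.9% | −2.1 |
| 40% | 49.3% | −0.7 |
| 50% | 50.0% | 0 |
| 60% | 50.7% | +0.7 |
| 100% | 53.5% | +3.5 |

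The largest shift is 3.5 / 1.21 = 2.9 half-widths.

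**3. When the rate leaves the stated interval.**
- Below 48.8%: q < (0.488 − 0.465) / 0.07 = 0.329, about 33%.
- Above 51.2%: q > (0.512 − 0.465) / 0.07 = 0.671, about 67%.

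**4. If fewer of the 490 qualify.** Some drop-outs may be untreated or lack a baseline score. Suppose only half (245) are treated, have a baseline score and lack a visit-2 score. The denominator is 6510 + 245 = 6755, and the FAS successes are 0.50 × 6510 = 3255.
- Worst case: 3255 / 6755 = 48.2%.
- Best case: (3255 + 245) / 6755 = 51.8%.
- The shift is 1.8 points, and 1.81 / 1.21 = 1.5 half-widths.

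**5. How few are enough.** The worst case reaches 48.8% when 3255 / (6510 + m) = 0.488, so m = 3255 / 0.488 − 6510 ≈ 160 patients, and 160 / 6670 = 2.4%.

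**6. Other missing shares (assumed; only 7% is in the protocol).** At p = 0.50 the bounds are 0.50(1 − d) and 0.50(1 − d) + d: 48.5% to 51.5% at 3%, 45.0% to 55.0% at 10%, and 42.5% to 57.5% at 15%.

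**The case against.** **Redaction.** The text of SAP 7.3 breaks off into redacted blocks straight after the sentence on the FAS, and the contents list shows further redacted headings. A sensitivity analysis could be there. This stands as a limit: only the readable text can be judged. What is readable points the other way, since Table 6.3:1 gives the primary endpoint to the FAS alone and SAP 6.6 rules out imputation beyond single items. If the analysis exists, the sponsor can point to it.

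**The bound can be worked out from planned output.** SAP 7.3 reports the number of successes, and the baseline tables will show the treated-set total, so a reader could divide one by the other. That comes close, but it is an unplanned calculation and its denominator includes treated patients with no baseline PF-10. The missing-data category required by SAP 7 does not help, because nobody in the FAS lacks the primary outcome.

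**The exclusion is open and agrees with the protocol.** SAP 4 declares the FAS as a new set, protocol 9.7.3 already excludes missing outcomes, and protocol 9.5 sizes the study on 6510 evaluable patients. This is right. The two documents do not conflict over the primary denominator; the gap is that neither tests its robustness.

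**The shift may be small and decides nothing.** For q between 40% and 60% it is at most 0.7 points, follow-up is only about 6 weeks, and 48.8% is a planning figure rather than a success criterion. All of that stands. It limits the seriousness of the point, but a result presented for its precision should still show the uncertainty that its interval omits.

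**Conclusion.** The concern holds. By SAP 6.3, 6.6 and 7.3 the primary rate is a complete-case figure at score level (a score with a few missing items is still computed), and no readable text plans an analysis of treated patients without a visit-2 score.

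At the planned drop-out, missing scores alone could move the rate by up to 3.5 points, against a stated half-width of 1.21. The ceiling requires all 490 to be treated, to have a baseline score, to lack a visit-2 score, and to be all non-successes or all successes. An optimistic FAS rate is likely if patients who do badly return less often, but the documents give no figure for this and the direction is not certain.

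The main analysis is not invalid. It would be reported with more precision than the data support, and that should be corrected.

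**What to change.** Keep the FAS rate as the main analysis and add to SAP 6.3 and 7.3:

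- A pre-specified sensitivity analysis in treated patients with a baseline PF-10, counting a missing visit-2 PF-10 as no therapeutic success, with best-case and worst-case bounds beside it.
- A table of the number of missing visit-2 PF-10 scores and the reasons, drawn from the removal reasons that protocol 9.7.4 already requires.
- A table of baseline characteristics for FAS patients against treated patients outside the FAS.

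The cost is SAP wording and two or three tables, with no new data collection. The sensitivity figure may be less favourable than the FAS rate. Because it counts administrative losses and incomplete questionnaires as failures, the report should present it as a bound and not as a competing estimate. If a redacted section already contains such an analysis, a reference to it would meet the first item.

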6.5 POOLING OF CENTRES

This section is not applicable because centre/country is not included in the statistical model.

6.6 HANDLING OF MISSING DATA AND OUTLIERS

In context of PF-10 questionnaire, missing values will be replaced with the mean of the other values, if less than half of the questions are missing for a patient. If half or more than half of the questions are missing, no score will be calculated and the PF-10 score will be marked as missing. No other missing data will be imputed.

6.7 BASELINE, TIME WINDOWS AND CALCULATED VISITS

Baseline visit (Visit 1) will include historical and demographic data as well as registration and initial examination. Treatment with Spiolto® Respimat® will be documented at visit 2 after approximately 6 weeks of treatment.

The mMRC breathlessness scale is completed by the patient at visit 1 and PF-10 questionnaire at visit 1 and 2 as well as satisfaction survey at visit 2. In addition, the PGE is completed by the physician at visit 1 and visit 2.

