9.2 SETTING

It is planned that data of approximately 7000 patients from approximately 750 sites in 11 countries will be collected. Site selection will be performed to reflect routine COPD care in the participating countries in order to secure representativeness of the COPD population. The following countries will participate in this non-interventional study: Russia, Romania, Hungary, Austria, Czech Republic, Bulgaria, Slovenia, Croatia, Israel, Slovakia, and Switzerland.

A log of all patients included into the study (i.e. having given informed consent) will be maintained in the Investigator Site File (ISF) irrespective of whether they have been treated or not.

Boehringer Ingelheim reserves the right to discontinue the study or to remove a patient at a particular study site for the following reasons:

1. Failure to meet expected enrolment goals overall or at a particular study site.
2. Emergence of any efficacy/safety information that could significantly affect continuation of the study, or any other administrative reasons, i.e. lack of recruitment.
3. Violation of the protocol, the contract, or applicable laws and regulations for non-interventional studies, which could disturb the appropriate conduct of the NIS.

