11.2 ADVERSE EVENT AND SERIOUS ADVERSE EVENT COLLECTION AND REPORTING

The investigator shall maintain and keep detailed records of all AEs in their patient files.

Collection of AEs

The study design is of non-interventional nature and the study is conducted within the conditions of the approved marketing authorisation. Sufficient data from controlled interventional trials are available to support the evidence on the safety and efficacy of the studied BI drug. For this reason the following AE collection and reporting requirements have been defined.

The following must be collected by the investigator in the eCRF from signing the informed consent onwards until the end of the study:

- all ADRs (serious and non-serious), related to Spiolto® Respimat®
- all AEs with fatal outcome (serious adverse events),

Note: For all patients on these data must be recorded on the AE pages in the eCRF. The separate NIS (S)AE form must in addition be used and forwarded to the local Pharmacovigilance as indicated in the form.*

All ADRs, including those persisting after study completion must be followed up until they are resolved, have been sufficiently characterized, or no further information can be obtained.

The investigator carefully assesses whether an AE constitutes an ADR using the information below.

Causal relationship of adverse event

The definition of an adverse reaction implies at least a reasonable possibility of a causal relationship between a suspected medicinal product and an adverse event. An adverse reaction, in contrast to an adverse event, is characterized by the fact that a causal relationship between a medicinal product and an occurrence is suspected.

Medical judgment should be used to determine the relationship, considering all relevant factors, including pattern of reaction, temporal relationship, de-challenge or re-challenge, confounding factors such as concomitant medication, concomitant diseases and relevant history.

Arguments that may suggest a **reasonable causal relationship** could be:

- The event is **consistent with the known pharmacology** of the drug
- The event is known to be caused by **or attributed to the drug class**.
- **A plausible time to onset of the event** relative to the time of drug exposure.
- Evidence that the **event is reproducible** when the drug is re-introduced

- **No medically sound alternative etiologies** that could explain the event (e.g. preexisting or concomitant diseases, or co-medications).

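### Does the SAP's wording of the treated set drop dosed patients who never reach visit 2?

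*SAP*

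**What the plan says.** Protocol 9.7.3: "All patients who have received at least one dose of Spiolto® Respimat® will be included in the analysis; this is the treated set". The same section ties the analyses to data recorded in the eCRF.

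SAP 6.3 defines the treated set as "All screened patients with informed consent, date of registration and at least one documented administration of" the study drug. The full analysis set (FAS) adds a PF-10 score at both visits. The treated set serves safety and baseline; the FAS serves the primary and secondary endpoints.

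SAP 6.7, describing the two visits, says that treatment "will be documented at visit 2 after approximately 6 weeks of treatment".

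The protocol also keeps untreated consenters in view. Section 9.1: "Baseline characteristics of patients being eligible and who gave Informed Consent, but were not treated in the study will also be collected". Section 9.2 has a log of all consented patients in the site file, "irrespective of whether they have been treated or not".

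On safety data, Protocol 11.2 says: "The following must be collected by the investigator in the eCRF from signing the informed consent onwards until the end of the study". The items are adverse drug reactions (ADRs) related to the study drug and all fatal adverse events.

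SAP section 4 lists only the FAS as a change from the protocol.

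**The concern.** The protocol's criterion is a fact (a dose was taken), whereas the SAP's is a record (an administration was documented). The one readable statement on where treatment is documented points to visit 2. Protocol Table 9.1:1 has no start-of-treatment item at visit 1 and marks the discontinuation and continuation items at visit 2 only. SAP 6.6 has no rule for missing administration data.

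Because the database also holds consented patients who were never treated, someone must sort the patients without visit 2 into treated and untreated. On a literal reading, a dosed patient who is then lost would be counted as untreated. Treated-set membership would depend on follow-up, and the set would shrink towards the FAS.

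ADR rates would be at stake. If reported events count as proof of dosing but nothing else does, event-free patients lost early leave the denominator and the rates are too high. If the lost patients' events go as well, the direction depends on their unknown risk.

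**Working it through.** **The plan's own figures.** Protocol 9.5 assumes a 50% success rate in 6510 patients. The 95% interval is 0.5 ± 1.96 × √(0.5 × 0.5 / 6510) = 0.5 ± 0.0121, or 48.8% to 51.2%, as stated. The drop-out step is 6510 / (1 − 0.07) = 7000, also as stated: "To account for a 7% drop-out rate, the sample size becomes 7000 patients".

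**Ceiling on the patients affected.** 7000 × 0.07 = 490. This is a ceiling because Protocol 9.5 does not define drop-out. The 7% may include patients never treated, or patients who attended visit 2 without a usable PF-10.

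**Case A: all events kept, a fraction f of the 490 removed from the denominator.** Relative error = 7000 / (7000 − 490f) − 1.

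| f (assumed) | Denominator | Relative error |
|---|---|---|
| 0.25 | 6877.5 | +1.8% |
| 0.5 | 6755 | +3.6% |
| 1 | 6510 | +7.5% |

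With an assumed 200 patients having an ADR, f = 1 moves the rate from 200/7000 = 2.86% to 200/6510 = 3.07%, about 0.2 percentage points.

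**Case B: all 490 removed together with their events.** Let k be the ADR risk of lost patients relative to completers. Relative error = 1 / (0.93 + 0.07k) − 1.

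| k (assumed) | Relative error |
|---|---|
| 1 | 0% |
| 2 | −6.5% |
| 3 | −12.3% |

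The documents give no value for f, k or the number of ADRs.

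**Does the text force the exclusion?** Five points, taken in turn:

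1. Protocol 9.7.3 already limits the analyses to eCRF data, so receipt of a dose always had to be shown by a record. The SAP wording puts the same criterion in operational form.
2. SAP 6.3 puts the two-visit condition in the FAS definition and omits it from the treated set. If the treated set were meant to depend on visit 2, this is where the SAP would say so.
3. SAP Table 6.2:1 removes patients from analysis sets only for lack of consent. Even a patient enrolled in breach of the follow-up criterion (exclusion criterion 4) is excluded from none.
4. Other records can show a dose. By the Protocol 11.1 definition an ADR is a response to the product, so a recorded ADR implies exposure. Protocol 9.7.3 plans to analyse reasons for ending treatment during observation and respiratory treatment during the study. Table 9.1:1 records concomitant medication and safety at visit 1 as well as visit 2.
5. Protocol 9.7.4 requires any removal from the analysis to be documented by site, patient and reason, and Protocol 9.6 provides missing-data checks and site queries. A patient should not vanish unnoticed.

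**Redaction.** The SAP contents list has a blacked-out heading directly after 7.6, starting on page 12, with the references on page 14. The abbreviations include treatment-emergent adverse events and the references include adverse-event handling guidance, yet no readable section covers adverse events. The safety analysis is probably behind the redaction, and exposure could be defined there. Its absence from the readable text cannot be held against the plan.

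**The case for a change.** The best case for acting is that the term is undefined in the readable text, the change of wording is not listed in SAP section 4, and two competent programmers could reach different treated-set counts. The log covering treated and untreated patients sits in the site file, while the analyses use the eCRF. None of the alternative records is named as sufficient, and a patient who was dosed, had no event and never returned may have none of them. A sentence or two would settle it at almost no cost.

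The lack of a definition and the omission from section 4 stand. The claim that dosed patients are excluded does not, because it needs SAP 6.7 to be read as an exclusive rule, which it does not state. The event-free patient who never returns is the hard case, but restoring the protocol wording would not solve it: without any record, nobody can tell whether that patient took a dose. Table 9.1:1 is a summary schedule, and the eCRF and data management plan are not among the documents, so a missing row there does not show a missing field. A separate unknown-exposure class with ADR rates shown both ways would be more apparatus than a descriptive study needs for this gap.

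**Conclusion.** The concern does not call for a change. The two definitions differ in wording, but the SAP's is the workable form of the protocol's, and no readable passage makes treated-set membership conditional on visit 2. A sensible analyst would count any eCRF evidence of a dose, including an ADR attributed to the drug.

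The effect is bounded and has no known direction. At most 490 of 7000 patients are involved, if the whole 7% allowance is dosed patients lost before visit 2. The error in ADR rates then runs from +7.5% (all 490 removed, all events kept) through zero (k = 1) to −12.3% (k = 3), with f and k assumed. All analyses are descriptive. The primary and secondary endpoints use the FAS, which requires PF-10 at both visits, so patients without visit 2 are outside those analyses under either wording. This judgement covers the readable text only.
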